4. RESEARCH QUESTIONS AND OBJECTIVES

The primary study objective is to evaluate the impact of the risk minimization measures on HCP and patient understanding regarding the risk of hypoglycemia and/or hyperglycemia due to medication errors associated with administration of Humalog U-200 KwikPen as communicated through the risk minimization measures.

The secondary objective is to evaluate behavior of HCPs and patients regarding the risk of hypoglycemia and/or hyperglycemia due to medication errors associated with administration of Humalog U-200 KwikPen as communicated through the risk minimization measures.

Specifically, this protocol refers to the surveys that are designed to assess the effectiveness of communications to HCPs and patients by assessing their understanding of the risks and safe use of Humalog U-200 KwikPen which were communicated through risk minimization measures including the following key safety messages:

HCPs:

- It is not necessary to adjust the insulin dose when switching from one strength of Humalog to the other
- Humalog U-200 KwikPen should not be transferred from the KwikPen to a syringe or insulin pump
- It is necessary to specify the Humalog strength on prescriptions
- It is necessary that patients always have a backup pen

Patients:

- It is not necessary to adjust the insulin dose when switching from one strength of Humalog to the other
- Humalog 200 units/mL should not be transferred from the KwikPen to a syringe as this could result in SEVERE OVERDOSE
- It is always necessary to carry a backup pen

The surveys are also designed to answer the following process research questions to assess the effectiveness of communications to HCPs and patients through the risk minimization measures. By testing a representative population about their knowledge and understanding of key safety message themes, we can generalize the:

HCPs:

- Extent of understanding of the key safety messages for Humalog U-200 KwikPen, as communicated through the DHPC (Were the key safety messages communicated in the DHPC understood by the HCP?)

- Extent of discussion between HCPs and patients when initially prescribing or dispensing Humalog U-200 KwikPen (Did the HCP convey the key safety messages in the label and DHPC to patients when they received their initial prescription of Humalog U-200 KwikPen?) with reference to the key safety messages.

Patients:

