5.9. Data analysis

Data collected from the survey will be reported as descriptive statistics. Frequency distributions with 95% CIs will be calculated for respondent responses to all questions that address the survey objectives. Responses to each question relating to the key safety messages will be categorized as “Correct response” and “Incorrect response”. “I don’t know” is categorized as an incorrect response unless otherwise specified.

In addition to the overall analysis, survey data will be analyzed to determine if there are any differences for HCPs, by medical specialty.

The following will be reported as part of the analysis:

HCPs:

Survey administration

- The number of survey invitations issued by method of distribution and specialty

- The number of survey invitations returned due to incorrect mailing address of HCPs invited to participate in the survey
- The number of HCPs who responded to the invitation to participate in the survey
- The number of HCPs eligible for participation in the survey
- The number of ineligible HCPs along with the reasons for ineligibility
- The number of eligible HCPs who completed the survey

Demographic characteristics of participants

- Distribution of participants by age groups
- Distribution of participants by gender
- Distribution of participants by practice setting
- Distribution of HCP by state
- Distribution of participants by medical specialty
- Distribution of participants by years in medical practice
- Distribution of participants by number of patients treated with Humalog U-200 KwikPen

Responses to questions pertaining to the survey objectives:

- Awareness of the DHPC on the correct use of Humalog U-200 KwikPen
- Understanding of the key safety messages
- Self-reported practices with respect to communication of the key safety messages in clinical practice

Patients:

Survey administration

- The number of invitations distributed
- The number of survey invitations returned due to incorrect mailing address of patients invited to participate in the survey
- The number of patients who responded to the invitation to participate in the survey
- The number of patients eligible for participation in the survey
- The number of ineligible patients along with the reasons for ineligibility
- The number of eligible patients who completed the survey

Demographic characteristics of participants

- Distribution of participants by age groups
- Distribution of participants by gender
- Distribution of patient by state

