	[RANDOMIZE LIST]	True	False	I don't know
A	Humalog® U-200 KwikPen® should only be injected using the prefilled KwikPen device in which it is supplied.			
B	Your dose of insulin does not need to be converted when changing from one strength of Humalog to the other (for example, changing from Humalog U-100 KwikPen to Humalog® U-200 KwikPen®).			

16. Please answer Yes, No, or I don't know for each of the following statements about the Patient Information Letter/*IMPORTANT SAFETY INFORMATION FOR* Humalog® KwikPen®, 200 units/mL, U-200 *insulin lispro* injection.

[RANDOMIZE LIST]		Yes	No	I don't know
A	The first time I was prescribed Humalog® U-200 KwikPen®, my doctor or nurse provided me with a paper copy of the Patient Information Letter/ IMPORTANT SAFETY INFORMATION . (This letter was included with the patient sample pen pack.)			
B	My doctor or nurse offered to explain information about the safe use of Humalog® U-200 KwikPen® the first time I was prescribed this product.			
C	I think about the important safety information for Humalog® U-200 KwikPen® to remind myself of the risks when injecting my insulin.			
D	I should always have a backup pen with me.			
E	It is ok to transfer insulin from the pen using a syringe.			

17. Other than the information you have received from your doctor or nurse, from what sources have you received and/or accessed information on the safe use and understanding of the Humalog® U-200 KwikPen®. (Please select all that apply.)

[RANDOMIZE LIST – KEEP OTHER AT THE BOTTOM]

- Pharmacist
- Other Healthcare Professional
- Diabetes Support Group
- Internet
- Product Warning Label
- Other

[TELEPHONE: BEGIN SAFETY EVENT/PRODUCT COMPLAINT – KEEP ON ONE PAGE]

(INTERVIEWER: Please record if respondent spontaneously reported a safety event or product complaint during the course of this interview.)

- Yes
- No **[GO TO CLOSING 1]**

Enter Safety Event or Product Complaint Verbatim

[MULTILINE INPUT]

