Correct Responses to Select PATIENT Survey Questions about Key Safety Messages for Humalog® U-200 KwikPen®

Q: Please answer True, False, or I don't know for each of the following statements about Humalog® U-200 KwikPen®.

STATEMENT	Correct Response
Humalog® U-200 KwikPen® should only be injected using the prefilled KwikPen device in which it is supplied.	TRUE
Your dose of insulin does not need to be converted when changing from one strength of Humalog to the other (for example, changing from Humalog U-100 KwikPen to Humalog® U-200 KwikPen®).	TRUE

Q: Please answer Yes, No, or I don't know for each of the following statements about the Patient Information Letter/IMPORTANT SAFETY INFORMATION FOR Humalog® KwikPen®, 200 units/mL, U-200 insulin lispro injection.

STATEMENT	Correct Response
The first time I was prescribed Humalog® U-200 KwikPen®, my doctor or nurse provided me with a paper copy of the Patient Information Letter/IMPORTANT SAFETY INFORMATION. This letter was included with the patient sample pen pack.	Yes
My doctor or nurse offered to explain information about the safe use of Humalog® U-200 KwikPen® the first time I was prescribed this product.	Yes
I think about the important safety information for Humalog® U-200 KwikPen® to remind myself of the risks when injecting my insulin.	Yes
I should always have a backup pen with me	Yes
It is ok to transfer insulin from the pen using a syringe.	No

If you have questions or are unclear about any of these responses, please refer to the Patient Communication on Important Safety Information for Humalog® U-200 KwikPen®.

**APPENDIX I.5 DIRECT HEALTHCARE PROFESSIONAL COMMUNICATION ON
THE CORRECT USE OF Humalog® KwikPen®, 200 units/mL**

**APPENDIX I.6 PATIENT COMMUNICATION: IMPORTANT SAFETY
INFORMATION FOR HUMALOG® 200 UNITS/ML KWIKPEN®
(INSULIN LISPRO)**

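### The patient answer key gives a correct answer to reports of receipt and behaviour, and two knowledge items are asked under a stem about the letter

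*Protocol*

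**What the plan says.** Section 4 gives patients three key safety messages. The first is "It is not necessary to adjust the insulin dose when switching from one strength of Humalog to the other". The second is "Humalog 200 units/mL should not be transferred from the KwikPen to a syringe as this could result in SEVERE OVERDOSE". The third concerns carrying a backup pen. Section 4 then sets separate research questions for understanding, for recall or receipt of the communication, and for considering the messages during administration. Sections 5.6 and 5.9 keep receipt, understanding and behaviour or practices as separate lines.

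Section 5.9 states the coding rule: "Responses to each question relating to the key safety messages will be categorized as" correct or incorrect. I don't know counts as incorrect unless stated otherwise. The section does not list the items to be coded.

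The patient key in Appendix I.3 is headed "Correct Responses to Select PATIENT Survey Questions about Key Safety Messages for Humalog® U-200 KwikPen". It has seven rows. Among those keyed Yes are 16A ("my doctor or nurse provided me with a paper copy of the Patient Information Letter/IMPORTANT SAFETY INFORMATION"), 16B ("My doctor or nurse offered to explain information about the safe use of Humalog® U-200 KwikPen® the first time I was prescribed this product") and 16C ("I think about the important safety information for Humalog® U-200 KwikPen® to remind myself of the risks when injecting my insulin").

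All five parts of Q16, including the backup-pen and syringe-transfer items, follow one instruction: "Please answer Yes, No, or I don't know for each of the following statements about the Patient Information Letter".

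**The concern.** Whether a letter was handed over, whether an explanation was offered, and what a patient thinks about while injecting are matters of fact about that patient. None has a correct answer. Some eligible patients will truthfully not answer Yes:

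- **16A:** eligibility rests on a filled prescription (Section 5.4.1), while the letter travels in sample packs (Section 3.1). Having received a sample is not required.
- **16C:** a patient who reports in Q8 not having used the pen yet is not screened out, and is still asked about injecting.

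If the key is taken as the coding list for Section 5.9, these answers would be tabulated as incorrect responses on key safety messages, against the Protocol's own separation of domains.

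The stem problem is different in kind. It sits in the instrument, so an analysis plan cannot repair it once data are collected. Understanding is the primary objective, and Section 5.3 judges the measures by whether a majority of respondents are aware of the messages. A stem that draws I don't know answers from patients who know the message would understate that awareness.

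**Working it through.** **The plan's own figures.** Equation 1 in Section 5.7 gives a half-width of 1.96 × √(p(1 − p)/280). For p = 50, 60, 70, 80 and 90% this is 5.86, 5.74, 5.37, 4.69 and 3.51 percentage points. Table 1 prints 5.9, 5.7, 5.4, 4.7 and 3.5, so it reproduces. Nothing in this point changes it.

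**The key set against the messages and domains.**

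| Item | Subject | Keyed answer | Patient message in Section 4 | Domain |
|---|---|---|---|---|
| 15A | inject only with the supplied pen | True | second, indirectly | understanding |
| 15B | dose when changing strength | True | first | understanding |
| 16A | letter received | Yes | none | receipt |
| 16B | explanation offered | Yes | none | exposure |
| 16C | thinks about the information | Yes | none | behaviour |
| 16D | backup pen | Yes | third | understanding |
| 16E | syringe transfer | No | second, directly | understanding |

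Four of the seven keyed statements test a message and three do not. As a description of the key only: a patient with all four knowledge items right who answers No to 16A to 16C matches 4/7, and a patient who answers True or Yes throughout matches 6/7, missing only 16E. The Protocol plans neither figure.

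**Comparison with the professional survey.** The key in Appendix I.1 lists only the four Q15 statements. Awareness, reading and discussion (Q16 to Q21) are left out. Transfer (Q15A) and backup pen (Q15D) are asked as True/False under a stem about the product. The patient survey departs from this model on both counts.

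**The stem.** 16D is the only patient item on the backup pen. 16E is the only one that names syringe transfer. Both share the letter stem, and the order within Q16 is randomized among the receipt items. Under Section 5.9, I don't know on either is incorrect by default.

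**Scale.** The Protocol gives nothing from which to estimate how many patients would be diverted. As a yardstick, each one lowers the item's rate by 1/280 = 0.36 points. At an observed 80%, where the half-width is 4.69 points, 13 diverted patients give 13/280 = 4.64 points and 14 give 14/280 = 5.00. So 14 of 280 would shift the rate by more than the half-width. This is a scale for reading the effect, not a forecast.

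**The case against.** The strongest reply is that the Protocol already places 16A to 16C outside understanding. They match none of the listed messages, and the coding rule reaches only questions about those messages. Receipt and behaviour have their own research questions and reporting lines. The key is described as an enclosure sent with the gift card after completion, not as a scoring specification. Section 5.10 says tables follow the survey analysis plan, which is not at hand and may assign items to domains.

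Much of this stands. A reader might infer that receipt and behaviour are counted as knowledge in the primary outcome, or that a patient's result would be 57% or 86%. The documents do not support that. Section 5.7 estimates a rate for each message, no total or average is defined, and miscoding 16A to 16C would leave the estimates for the other four items untouched. A reader might also infer that patients are mailed a verdict on their own answers, but the sheet is generic. Nor does failed distribution become inseparable from failed comprehension, since receipt has its own item and reporting line and Section 5.11 acknowledges the distinction.

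What remains is that the key's heading uses the same term as the coding rule, the rule names no items, and no other place defines a correct patient answer.

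On the stem, it can be said that 16D and 16E make sense without the letter, that a preamble says the questions concern the product, and that the survey was user-tested with 9 patients. These points lower the likelihood of a large effect. They do not remove the defect: the preamble is displayed with Q15, while Q16 has its own instruction naming the letter. The Protocol does not report whether testing covered this stem.

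**Conclusion.** The concern holds in two limited parts.

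1. The patient key conflicts with the Protocol's separate receipt, understanding and behaviour domains in three of its seven rows. With the unlisted scope of Section 5.9, it leaves open whether those three items are coded correct or incorrect. This is an ambiguity in the text, not a shown error in any planned estimate.

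2. The letter stem may lower the measured rate for the backup-pen message and for the direct syringe-transfer item. The direction rests on the assumption that some patients who did not see the letter would choose I don't know although they know the message. The size is unknown. The dose message (15B) and the indirect device item (15A) are not exposed.

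Both parts should be settled before fielding, because the stem cannot be corrected afterwards.

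**What to change.** - In Section 5.9, state that for patients only 15A, 15B, 16D and 16E are coded correct or incorrect.
- Move 16D and 16E into the Q15 True/False block under its product stem, as the professional survey does. The keyed answers become True for the backup pen and False for syringe transfer.
- Report 16A and 16B as receipt or exposure and 16C as self-reported behaviour, each as Yes/No/I don't know frequencies with no correct category.
- Delete 16A to 16C from the mailed key.

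The cost is a small re-programming of the survey, one edited mailing and a sentence in Section 5.9. The revised survey may need to go back to the central IRB named in Section 6.3. No extra respondents are needed.
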